- Overdose History: This assessment asks patients if they have ever overdosed on a substance and then goes into branching logic for details of the incident if they have, with questions like "when?", what substance, etc.
- First Response Opioid Survey Tool (FROST): This survey has questions for all research participants about the first time they used opioids.

7.2.2 Week 4 (+/- 2 weeks), Week 8 (+/- 2 weeks), Week 12 (+/- 2 weeks), & Week 24 (+2/- 4 weeks)

The same procedures and measures listed above will be repeated again at the Week 4 (+/- 2 weeks), 8(+/- 2 weeks), 12(+/- 2 weeks) & 24(+2/- 4 weeks) follow up visits – measured from completion of baseline questionnaires and randomization. Given the predicted scheduling challenges with this population, we plan to incorporate a 2-week window for completion of specific visits. For the last visit, we plan to allow for a +2/-4 window in the event that we need to allow for time to locate specific subjects who have been lost to follow-up.

A qualitative interview will be conducted and recorded with patients who have been assigned to TAU + reSET-O (n=100) at week 4 to gather their initial thoughts on the app and identify factors contributing to time spent on the app. Qualitative interviews will also be conducted at weeks 8 and 12 to elicit personal accounts of their experience using the program, acceptability of the program, and suggestions for improvement. The total time to administer these qualitative interviews is estimated at 20-30 minutes. The interview will be audio recorded. The audio recording will be stored on the Hershey Network server, accessible only by assigned study staff and the PI. The interview does not ask for PHI and therefore PHI is not expected to be in the recording; however, transcriptionists will be trained to remove PHI from any interviews.

reSET-O only works for 12 weeks at a time. Therefore, at week 12, subjects who have been randomly assigned to TAU + reSET-O will repeat the reSET-O enrollment process again, which includes the PSC form, for the continuation of their access to reSET-O. Information on the first enrollment form will be identical to the second enrollment form, with the exception of phone number and email in the event that this information has changed. There is no change in

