8.3 Statistical methods

Outcome Measures and Covariates

Primary outcome: The primary outcome will be a binary indicator of whether or not the patient is retained on MAT (methadone, buprenorphine, or buprenorphine-naloxone) treatment through 24 weeks. For those who drop out before 24 weeks, time (week) of dropout will be recorded, and they will be considered as not retained.

Secondary outcomes: 1) weeks of treatment retention (time to drop-out 0-24 weeks, survival; number of weeks retained, continuous); 2) urine-confirmed abstinence from opioids in the last 4 weeks (longitudinal (weeks 4, 8, 12, and 24), binary); 3) Days using opioids in the last 4 weeks (longitudinal, continuous); 4) Days using other drugs/alcohol in last 4 weeks (longitudinal, continuous); 5) coping strategies (CSS mean score; longitudinal, continuous); 6) social functioning (EuroQol, SCS, global scores and subscales; longitudinal, continuous); 6) overall mental health symptoms (K10; longitudinal, continuous); 7) HIV risk behavior—days in past 30 of vaginal or anal sex without a condom (longitudinal, continuous); Any needle sharing in past 4 weeks (longitudinal, binary); 7) Treatment satisfaction at week 24 (IAFF; continuous); 8) Serious adverse events (binary).

Additional variables: *Covariates, primary and secondary analyses:* Stratification factors: 1) any intravenous drug use (binary); 2) treatment with methadone vs buprenorphine at Hub vs buprenorphine at Spoke (categorical). *Moderators:* 1) both stratification factors will be explored as moderators; 2) demographic characteristics (gender, age, ethnicity etc.); 3) prescription opioid use only vs any heroin or fentanyl use (binary); 4) other substance use at baseline (any cannabis, any stimulant, any heavy drinking days; binary); 5) Probable major depression at baseline (binary based on PHQ score); 6) history of prior treatment for opioid use versus first treatment episode (binary). *Mediators:* 1) social functioning (EuroQol; continuous); 2) social connectedness (SCS; continuous); 3) opioid craving (continuous); 4) coping (CSS; continuous); and 5) mental health symptoms (K10; continuous).

Intent to Treat, Dropouts, and Missing Data

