All analyses will be on the Intent-to-treat (ITT) sample, i.e., all randomized subjects (N=200) according to the treatment arm to which they were assigned. For the primary outcome, patients that dropped out before 24 weeks will be considered not retained. For the secondary outcome urine-confirmed abstinence, missing data (patients who cannot be located) will assumed to be opioid positive (not abstinent), a typical assumption which is reasonable based on the high rate of relapse among patients with OUD who discontinue medication treatment (Weiss et al., 2011; 2015; Hser et al., 2016; 2017). For other secondary outcomes, missing data will be treated as missing at random. Longitudinal mixed effects models do not require complete data to provide estimates of the outcome, and the estimates are considered valid under the assumption that the data are missing at random (Little & Rubin, 2002). We will additionally perform sensitivity analysis for the secondary outcomes to examine the influence on the outcomes of dropout and missing data by performing several imputation methods, for instance imputing missing weeks as all abstinent or all non-abstinent. Comparison of the inferences from assuming various models for the missingness provides a measure of the validity of the efficacy estimate from the initial model.

Significance Testing and Preliminary Analyses

All tests for main effects will be performed at two-sided significance level of 5%. Before performing specific analyses, we will examine the distribution of outcome measures and covariates and investigate for outliers. The distributions of continuous variables will be checked for normality, and transformed, if necessary. Distribution of demographic variables will be examined and described in terms of means, standard deviations, proportions and 95% confidence intervals. Covariates will be examined for association with treatment outcome. Covariates associated with treatment outcome will be adjusted for in models used to test study hypotheses.

Primary outcome

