Statistical Model: *Hypothesis: Adding reSET-O to TAU (reSET-O + TAU arm) will promote greater 24 week retention in treatment on buprenorphine compared to the TAU arm.* The positive effect of randomization to the reSET-O+TAU group compared to TAU group will be estimated using logistic regression with the binary outcome of retention in treatment for 24 weeks (yes/no) modeled as a function of treatment condition (reSET-O + TAU vs TAU) and stratification factors (methadone treatment; buprenorphine treatment at Hub; buprenorphine treatment initiation at hub and continuation at spoke) and intravenous drug use in last 30 days (yes/no). The odds ratio of the treatment term and its confidence limits will estimate the treatment effect. The raw retention rates in each treatment group and rate differences will be computed for descriptive purposes.

Secondary outcomes

Statistical Models: For each of the secondary outcomes (see above) the effect of randomization to the reSET-O+TAU arm compared to the TAU arm will be estimated with a model of the same general form as for the primary outcome (three independent variables: treatment assignments (reSET-O+TAU vs TAU) and the two stratification factors) using logistic regression model (for binary outcomes), generalized linear model (for continuous outcomes), or longitudinal generalized mixed effects model (for longitudinal outcomes) with appropriate link functions (e.g. logit for binary outcomes). Longitudinal outcomes analyzed using a mixed effects models will utilize a generalized estimating equation with an autoregressive correlation structure to account for within subject correlation over time, as well a random intercept accounting for between subject variability. Retention data will be displayed with Kaplan-Meier curves that show the observed probability of retention in the program until time t, over time across the 24-week trial. The time to not-retained (dropout) data for reSET-O +TAU and TAU groups will be analyzed using proportional hazards models with covariates. If proportional hazard assumption is not satisfied, the data will be analyzed using a non-parametric log-rank test. In addition to stratification factors, covariates that are found to be related to the outcomes will be also added to the models to improve the power for detecting significant differences.

Moderation and Mediation

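### Section 8.3 gives the longitudinal secondary outcomes a GEE and a random-intercept mixed model at once, with no visit term, so the odds-ratio scale, the missing-data basis and the visit weights are open

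*Combined protocol and SAP*

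**What the plan says.** Section 8.3, under Secondary outcomes, assigns repeated measures to a "longitudinal generalized mixed effects model (for longitudinal outcomes) with appropriate link functions (e.g. logit for binary outcomes". The next sentence says these models will use a "generalized estimating equation with an autoregressive correlation structure to account for within subject correlation over time, as well a random intercept". The listed terms are "three independent variables: treatment assignments (reSET-O+TAU vs TAU) and the two stratification factors"; covariates found to be related to the outcome may be added, but neither visit nor treatment-by-visit is named.

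The visit schedule appears in the outcome list: "urine-confirmed abstinence from opioids in the last 4 weeks (longitudinal (weeks 4, 8, 12, and 24), binary". No week or average is named there as the treatment comparison.

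On missing data, section 8.3 handles urine-confirmed abstinence separately: "missing data (patients who cannot be located) will assumed to be opioid positive (not abstinent". For the other secondary outcomes it appeals to longitudinal mixed effects models, for which "the estimates are considered valid under the assumption that the data are missing at random". It adds sensitivity analyses by "performing several imputation methods, for instance imputing missing weeks as all abstinent or all non-abstinent".

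Section 9.7 refers back to section 8.3 for the detailed analysis plan, so nothing elsewhere settles these points.

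**The concern.** A GEE models the population-average mean and treats within-patient correlation as a working assumption. A mixed model with a random intercept conditions on a patient effect. The analyst has to choose one, and the text supports both.

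The choice has different consequences by outcome type. For urine abstinence and needle sharing it changes what the odds ratio means. For the continuous outcomes (opioid days, other drug and alcohol days, coping, social functioning, K10, HIV risk days) both readings estimate the same mean difference, but the missing-at-random justification belongs to the likelihood-based model.

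Separately, without visit terms the model condenses four unequally spaced visits into one number whose weights follow from the covariance. An effect gone by week 24 and one largest at week 24 can then look alike. Section 9.7 passes the data to the analysts after data lock, so choices left open now would be made with the data in hand.

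**Working it through.** **The plan's own figure.** Section 8.2 gives 100 per arm, 80% power, two-sided 5%, 40% against 59.7%. The pooled two-proportion formula returns 100 per arm and 80.03% power, and (0.597/0.403)/(0.40/0.60) = 2.22. This concerns the primary outcome only and is untouched by what follows. The documents give no covariance, prevalence or rate of missing assessments for the longitudinal outcomes, so every input below is an assumption.

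**1. Odds-ratio scale.** In a random-intercept logistic model with intercept SD s, the population proportion is P(b) = ∫ expit(b + s·z) φ(z) dz. Choose b0 so that P(b0) = 0.40, then evaluate P(b0 + ln 2.22). The 40% and 2.22 are borrowed from section 8.2 as illustration.
- s = 1: P = 0.5633; marginal OR = (0.5633/0.4367)/(0.40/0.60) = 1.93.
- s = 2: P = 0.5196; marginal OR = (0.5196/0.4804)/(0.40/0.60) = 1.62.
- In reverse, 40% against 59.7% (marginal 2.22) is a conditional OR of 2.62 (s = 1) or 3.72 (s = 2).

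**2. Visit weights of the pooled coefficient.** With complete data and no visit term, the weights are w = V⁻¹1/(1′V⁻¹1). For an autoregressive V this is proportional to 1/(1+r) at the end visits and 1/(1+r_left) + 1/(1+r_right) − 1 at the inner ones.

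| Assumed V | Unscaled values | Weights, weeks 4/8/12/24 |
|---|---|---|
| Exchangeable | equal | 25/25/25/25% |
| AR by visit order, r = 0.5 | 0.667, 0.333, 0.333, 0.667 (sum 2) | 33/17/17/33% |
| AR in actual weeks, 0.7 per 4 weeks (r = 0.7, 0.7, 0.7³ = 0.343) | 0.588, 0.176, 0.333, 0.745 (sum 1.842) | 32/10/18/40% |

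Apply these to two opposite assumed patterns: rising, 0.40 × week/24, giving 0.067, 0.133, 0.200, 0.400 SD; and fading, 0.40 × (24 − week)/24, giving 0.333, 0.267, 0.200, 0 SD.

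| Assumed V | Rising | Fading |
|---|---|---|
| Exchangeable | 0.20 | 0.20 |
| AR by visit order | 0.21 | 0.19 |
| AR in actual weeks | 0.23 | 0.17 |

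The week-24 effects are 0.40 and 0. The pooled coefficient reports nearly the same number for both patterns.

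**3. GEE against mixed model under missing at random.** Simulation with 100 per arm, SD 1, true constant effect −0.40, no visit term, and dropout depending on the last observed value. With equal dropout mechanisms in the arms, or an autoregressive truth, GEE-AR(1) stays within 5% of the truth and the two readings differ by at most 0.018 SD. Only with an exchangeable truth and dropout mechanisms that differ by arm does GEE-AR(1) shrink, to between −0.372 and −0.338. That is (0.40 − 0.372)/0.40 = 7% to (0.40 − 0.338)/0.40 = 16%, against 0–2% for random intercept plus AR. Urine abstinence is outside this point, because missing is set to positive.

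**4. Time trend common to both arms.** If the arms lose different shares of late visits, their pooled means weight the common trend differently, and the difference enters the treatment coefficient. Simulated with zero true effect and 1,000 replicates per setting:

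| Fall from week 4 to week 24 | Missing by arm | False effect | Type I error |
|---|---|---|---|
| 1.0 SD | 50% vs 20% | about −0.09 SD | 10–12% |
| 1.0 SD | 30% vs 15% | −0.04 SD | 4–8% |
| 0.5 SD | 50% vs 20% | −0.04 to −0.05 SD | 6–7% |
| 0.5 SD | 30% vs 15% | −0.02 SD | 4–5% |

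With visit terms the false effect is within 0.006 SD and the error rate 4–6.5%.

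**The case against.** Four points on the other side carry weight.

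First, a reader might infer that the target is wholly undefined. It is not. Section 8.3 gives the secondary models the same general form as the primary one and speaks of tests for main effects, which implies a visit-pooled treatment coefficient. What is open is its weighting, and it is nowhere stated as the intended contrast.

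Second, a reader might infer that week 24 should be the target because "reSET-O only works for 12 weeks at a time" and patients re-enrol at week 12. Section 7.2.2 goes on to say that the account rolls over, with modules and contingency management unchanged, so the documents do not make week 24 different in kind. Choosing week 24 also costs precision: for a constant effect of 0.40 SD, correlation 0.5 and 20% missing, power is about 75% against 94% for the four-visit average.

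Third, the mixed-model reading is favoured by the missing-data text, and for continuous outcomes the practical gap is small in most settings. That stands. It does not settle the scale for the binary outcomes.

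Fourth, large differential loss of assessments is not a given. The plan follows patients who have left treatment, using a locator form, calls at weeks 16 and 20 and a wide week-24 window. The trend leak should therefore be read as modest unless both the imbalance and the trend are large.

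The planned sensitivity analyses vary the imputation; they choose neither model nor contrast.

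**Conclusion.** The point holds in a limited form. The three labels cannot describe one fit, and no other section resolves them. The firmest consequence is for urine abstinence and needle sharing, where a reported odds ratio could be on either scale (2.22 conditional against 1.93 or 1.62 marginal, for assumed SDs of 1 or 2 and a 40% control rate). For continuous outcomes the issue is the missing-data justification, and its effect is small unless dropout mechanisms differ by arm. The single pooled coefficient has weights that the plan does not fix, cannot show whether an effect is early or late, and can absorb some common time trend if missingness differs by arm.

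The documents do not support saying that these analyses have no target, that they are generally biased, or that week 24 must be the comparison. The primary analysis and the sample size stand. The correction should be made before the data are released for analysis.

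**What to change.** Replace the GEE sentence in section 8.3 with one named model per outcome type.

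- **Continuous outcomes:** likelihood-based linear mixed model with treatment, visit (weeks 4, 8, 12, 24), treatment-by-visit, the two stratification factors and, where collected, the baseline value of the outcome. Unstructured covariance; if it does not converge, random intercept plus correlation decaying in actual weeks.
- **Binary outcomes:** name one model with the same visit terms, use the same odds-ratio scale for urine abstinence and needle sharing, say whether it is marginal or conditional, and state the missing-data assumption that goes with it. If needle sharing is sparse, drop treatment-by-visit and report the visit-adjusted pooled odds ratio. With an assumed 75 observed per arm at week 24, the chance that at least one arm has no events is 1 − (1 − (1 − p)^75)², which is 4%, 19% or 39% at a prevalence p of 5%, 3% or 2%.
- **Target contrast:** state either the equally weighted four-visit average (closest to the present text) with the week-24 difference alongside, or the week-24 difference with the average as supportive. The choice is the sponsor's, given the precision trade-off.

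The cost is SAP wording, standard software and a few more parameters to estimate. No new data, visits or patients are needed.

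### The log-rank fallback for time to dropout adds no protection against non-proportional hazards, and as written it drops the stratification factors and gives no effect estimate of its own

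*Combined protocol and SAP*

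**What the plan says.** Section 8.3 (Outcome Measures and Covariates) lists as the first secondary outcome "weeks of treatment retention (time to drop-out 0-24 weeks, survival; number of weeks retained, continuous"). Dropout is dated by week: "time (week) of dropout will be recorded".

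Under Secondary outcomes, the same section sets one general form for every secondary model: "three independent variables: treatment assignments (reSET-O+TAU vs TAU) and the two stratification factors". Time to dropout in the two arms "will be analyzed using proportional hazards models with covariates". The next sentence is the fallback: "If proportional hazard assumption is not satisfied, the data will be analyzed using a non-parametric log-rank test". The paragraph closes by saying that, beyond the stratification factors, "covariates that are found to be related to the outcomes will be also added to the models to improve the power". Kaplan-Meier curves are shown whichever test is used.

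The section does not say how proportionality will be checked or what result triggers the switch. Nor does it say whether the log-rank test is stratified or weighted, or what effect measure goes with it.

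**The concern.** A fallback should be less dependent on the assumption that failed. This one is not. The log-rank test weights all dropouts equally over time, as the Cox score does, so early and late differences of opposite sign cancel in both. The switch therefore leaves the problem in place and gives up two things the adjusted model had: the stratification factors and an estimate with an interval. Because no diagnostic or threshold is stated, the choice of test is also made after the data are seen.

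At stake is the clarity, and some of the power, of one secondary outcome.

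**Working it through.** **1. The plan's own figure.** Section 8.2 gives 100 per arm, 40% vs 59.7% retained, 80% power, two-sided 5%. With pooled variance under the null:

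n = [1.96 × √(2 × 0.4985 × 0.5015) + 0.8416 × √(0.40 × 0.60 + 0.597 × 0.403)]² / 0.197² = (1.386 + 0.583)² / 0.0388 ≈ 100 per arm.

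Power at 100 per arm is 80.0% and the odds ratio is 2.222, so the stated size reproduces. The plan gives no power for time to dropout. Under proportional hazards the same rates imply HR = ln 0.597 / ln 0.40 = 0.563 and about 60 + 40.3 = 100.3 dropouts. The Schoenfeld power is then Φ(√(100.3/4) × |ln 0.563| − 1.96) = 82%.

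**2. The identity.** At each dropout time j, let d be the dropouts, n the number at risk, and d₁, n₁ the same counts in one arm.
- Log-rank: U = Σ(d₁ − d·n₁/n), V = Σ d(n₁/n)(1 − n₁/n)(n − d)/(n − 1).
- Treatment-only Cox score at zero effect (Breslow): the same U, and the same V without the factor (n − d)/(n − 1).

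Without ties d = 1, the factor is 1, and the tests coincide. On one simulated trial both chi-squares were 14.354. With the times rounded up to weeks they were 14.25 and 13.88, and the gap comes only from that factor.

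**3. Behaviour across hazard shapes.** The settings were 100 per arm, constant TAU hazard giving 40% at week 24, a change point at week 12, censoring only at week 24, and 2,000 trials per shape. The shapes are assumptions; the documents give none.

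| Shape | Retained at 24 weeks (TAU vs reSET-O + TAU) | Log-rank | Unadjusted Cox | Mean weeks retained |
|---|---|---|---|---|
| Proportional | 40% vs 59.7% | 81% | 81% | 74% |
| Effect only after week 12 | 40% vs 59.7% | 60% | 59% | 17% |
| Effect only before week 12 | 40% vs 59.7% | 94% | 94% | 100% |
| Crossing, early benefit (HR 0.4, then 1.6) | 40% vs 40% | 11% | 11% | 57% |
| Crossing, early harm (HR 1.6, then 0.4) | 40% vs 40% | 11% | 11% | 34% |
| No effect | 40% vs 40% | 6% | 6% | 6% |

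Log-rank and unadjusted Cox reached the same 5% decision in 99.35% to 99.95% of trials. The Monte Carlo standard error at 5% is √(0.05 × 0.95 / 2000) = 0.5 points, so the 6% in the last row is about two standard errors high for all three tests alike. A separate null run with a covariate gave 5.1%.

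**4. What is lost against the planned, adjusted model.** With one covariate of HR 1.65 per SD, power for log-rank / adjusted Cox / adjusted mean weeks was:
- break at week 8: fading effect (0.4 then 1.0) 33% / 39% / 62%; reversal (0.4 then 1.3) 8% / 10% / 32%; delayed effect (1.0 then 0.45) 44% / 47% / 23%. An independent repeat was close: 33% / 40% / 59%, 9% / 10% / 32% and 43% / 45% / 21%.
- break at week 12: fading 58% / 67% / 85%; reversal 30% / 37% / 73%; delayed 23% / 25% / 11%.

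Adjusted Cox thus leads log-rank by 1 to 9 points. That covariate is strong: for a 50:50 binary factor (SD 0.5) it equals HR 1.65² ≈ 2.7. Using the plan's own kind of factors (one binary, one three-level), the difference was 0.0 to 2.4 points at HR 1.3 to 1.65 and 5 to 12 points at HR 2.7.

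**The case against.** Four points on the other side carry weight.

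- **An estimate exists elsewhere.** A reader might infer that a fading benefit would end in a p-value alone. The documents do not support that. Weeks retained is a separate continuous form of the same outcome ("number of weeks retained, continuous"). It gets its own model with treatment and both stratification factors, and that analysis does not depend on the proportionality check. If every dropout week to week 24 is known, it is the restricted-mean difference. Kaplan-Meier curves also appear regardless. What is missing is any statement that this is the estimate to rely on when proportionality fails.
- **The log-rank test is valid.** A reader might infer a false-positive problem. There is none: under equal hazards the test holds its size, and the switch does at least stop a single hazard ratio being read as the effect.
- **The fallback is not literally the planned test.** It matches a treatment-only Cox model, whereas the plan's model is adjusted. The near-perfect agreement in step 3 concerns the unadjusted model only.
- **No alternative dominates.** Mean weeks retained gains under crossing hazards but loses badly under a delayed effect (17% vs 60%). That argues against making it the test.

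It might also be said that the closing covariate sentence carries the stratification factors into the log-rank test. That sentence speaks of adding terms to models, and nothing in the fallback mentions strata, so the SAP should not leave this to be inferred.

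Finally, the 12-week app renewal in section 7.2.2 might suggest that non-proportional hazards are likely. The same section says that access rolls over with modules and contingency management unchanged, so it establishes no particular hazard shape.

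**Conclusion.** The point stands as a minor one. If followed, the rule replaces an adjusted analysis with one that is no more robust to non-proportional hazards, omits the stratification factors as written, and has no estimate attached. The identity with treatment-only Cox is exact without ties and close with weekly ties.

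The cost is modest: about 0 to 2 points of power against adjusted Cox with weak covariates and up to about 12 with strong ones. That range rests on assumed covariate strengths and hazard shapes. The much larger contrasts with mean weeks retained depend on the hazard shape and reverse for a delayed effect, so they do not measure the harm done by the switch.

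**What to change.** In section 8.3, delete the conditional switch and state:

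1. One prespecified test of time to dropout that uses the stratification factors: either the adjusted Cox model or a log-rank test stratified by those factors. It applies whatever the proportionality check shows.
2. How proportionality will be examined, for description only.
3. If hazards are not proportional, no single hazard ratio is interpreted. The effect estimate is the adjusted difference in weeks retained to week 24 with its confidence interval, supported descriptively by hazard ratios for weeks 0-12 and 12-24.

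If the stratified log-rank is chosen, fix the list of factors first: section 8.3 names intravenous drug use as a stratification factor, but section 7.4.3 mentions only the three-level medication and setting factor. Both together give 2 × 3 = 6 strata, about 200/6 ≈ 33 patients each on average.

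The cost is a few lines of SAP text and code, with no new data. The trade-off is that mean weeks retained is insensitive to a delayed effect, so it serves as the estimate and does not replace the test.
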